Sample size calculation is determined by the primary research question: does treatment with metformin result in a gain in the length of gestation of greater than or equal to 5 days compared to the mother receiving placebo therapy. For each mother her gestational age at diagnosis (trial enrolment) sets the maximum allowable length of pregnancy prolongation. For those with PE diagnosed at 31+6 will be delivered at 34 weeks (should they reach that gestation, as it is unit policy to deliver at that gestation) thus setting a ceiling for maximal prolongation of 15 days. Therefore, the maximum potential gestation prolongation is 63 days for stratum 1 and 42 days for stratum 2 mothers. The primary outcome will be the median prolongation of gestation, reflecting the skewed distribution of the gestation prolongation seen in published clinical trials.¹ The researchers believe that median prolongation a more clinically meaningful measure of change than either raw mean or ratio change. Sample size calculations were based upon the Geometric Mean Ratio (GMR), an appropriate measure for differences in median. Analysis was performed both using PASS 13 (Power Analysis and Sample Size Software (2014). NCSS, LLC. Kaysville, Utah, USA, ncss.com/software/pass) and the Powercal program running in Stata v15 (Stata statistical software. 2017 Release 15. Stata Corp. College Station, TX: StataCorp LLC).

Power calculations settings were: 90% power, with two-sided alpha set at 0.05, median prolongation of 8.3 days in the control arm and a clinically important gestation prolongation of 5 days. The measure of variability used in this analysis is the coefficient of variation (CV) in mothers treated with standard expectant

¹ Hall DR, Odendaal HJ, Kirsten GF, et al. Expectant management of early onset, severe pre-eclampsia:

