management (control group). Two studies were used provided estimates for the expected gestational prolongation and associated CV in pre-eclamptic mothers receiving expectant management after PE diagnosis (control group) on two studies ². The first by Hall et al reported a mean gestation prolongation of 11 (SD 7) days equivalent to a CV = 0.64, whilst the second by [name] et al (PIE 1 study) reported an overall mean prolongation of 13.1 (SD 12.2) days in the placebo arm, a CV = 0.93. In the PIE 1 study mothers entering at a gestation greater than 29 weeks had a CV = 0.8. We have chosen to use a CV = 1.0, slightly larger than the 0.93 found in the overall PIE study, to maintain adequate power if slightly greater variability in prolongation times occurs. The results of sample size estimates for a limited range of GMR and two CVs are presented in the following table:

Detectable prolongation in median days*	Treated group Median	GMR	Number per group (CV = 1.0)	Number per group (CV = 0.93)	Number per group (CV = 0.80)
3.11	11.43	1.37	137	134	105
4	12.32	1.48	88	87	69
5	13.32	1.6	65	61	49

*placebo group median = 8.32 days

Therefore, at analysis we require 65 patients per trial arm. Allowing for 10 dropouts within each arm we plan to recruit 150 patients (75 patients in the placebo & 75 in the treatment arms). The dropouts, including patient requested trial withdrawal and delivery before any trial medication was given occurred in 6/119 (5.0%) of mothers.

Whilst presentation of results will include Kaplan-Meier survivorship curves and adjusted hazard ratios for a Cox proportional hazards model the following power analysis based upon expected events indicates that this study is not adequately powered to use survivorship as the primary endpoint. In the setting of this trial the Hazard Ratio (HR) defined as the time for control/time for Rx at the same proportion of survival. For example, taking the median survival time of 9 days in the control group from the Hall study we can assess the HR detected for the predetermined group size:

Time above median (days)	Median time in Rx group (days)	HR	Group size (equal group size)
3	12	0.75	360
4	13	0.69	225
5	14	0.64	158
6	15	0.60	120
7	16	0.56	96
8	17	0.53	80
9	18	0.50	68
13.5	22.5	0.40	42

² [name] CA, Hannan NJ, van Papendorp E, et al. Esomeprazole to treat women with preterm preeclampsia: a randomized placebo-controlled trial. Am J Obstet Gynecol 2018;219:388.e1-17

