Given the sample size of 65 per arm this study has a power of 0.9 to detect a difference of 9 days which translates to an ability to detect only a Hazard Ratio ~ 0.5 or smaller.

All secondary outcomes are binary with expected incidence less than 0.05. At the projected sample size of 65 the power to detect a 50% change in incidence is low at 0.12.

12. Framework

This trial uses a superiority hypothesis testing framework between treatment groups for all outcomes.

13. Statistical Interim analyses and stopping guidance

This is a phase II trial with mothers under direct in hospital observation which facilitates immediate detection and management of adverse events. For the planned sample size only a very large treatment effect size would lead to an indication to cease the trial for efficacy at information fraction of 60 – 80%. Given the phase II nature of the study, the complete observation of mothers whilst under trial treatments, there is no planned interim analysis for efficacy. There is no planned interim assessment for futility. The DMC will monitor for adverse events and will provide stopping guidance should this be deemed necessary. See separate DMC charter (PI2 DMSC Charter version 16 June 2018).

14. Timing of final analysis

Unblinding and final analysis will be performed only after all participants have being delivered and all neonatal follow-up has been completed. Neonatal death is one of the outcomes within the prespecified composite neonatal outcome (see protocol p 38 – 39) and is assessed at six weeks post-delivery. Therefore, analysis is will not commence prior to six weeks after the delivery of the last recruited trial patient. Publication of biomarker results may be published separately from the clinical trial outcomes.

15. Timing of outcome assessments.

The primary outcome is measured from time of randomization to delivery. Secondary maternal and neonatal composite outcomes are measured from time of recruitment until six weeks after the due date, with timing dependent upon outcome measures.

Section D: Statistical Principles

16. Confidence intervals and p-value

The significance level is set at 0.05 and all hypothesis testing will be two-sided. A single primary outcome is tested at a significance level of 0.05. If and only if a significant difference is found will the secondary outcomes be tested. The two secondary outcomes will each be tested at a significance level of 0.025.

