Composite secondary outcome definitions:

(i) Maternal composite outcome: the occurrence of any of the following serious maternal outcomes: maternal death, eclampsia, pulmonary oedema (oxygen saturation $\leq 90\%$, with clinical symptoms requiring treatment), severe renal impairment or the need for dialysis, a cerebral vascular event, placental abruption and liver haematoma or rupture.

(ii) Neonatal composite outcome: the occurrence of any of the following serious neonatal outcomes: neonatal death within 6 weeks after the expected due date, grade III or IV intraventricular haemorrhage, necrotizing enterocolitis and bronchopulmonary dysplasia

Exploratory outcomes:

All other outcomes, including outcomes nested within individual secondary outcomes or outcomes with less clinical interest than secondary outcomes are classified as exploratory outcomes. These will not be subject to hypothesis testing, but precision of point estimates and may be presented using unadjusted 95%CI.

24. Statistical Analysis methods

Raw data primary outcome:

For raw results data, the primary outcome will be summarized using median [25th – 75th percentile] along with minimum and maximum values. All secondary outcomes and exploratory outcomes of interest will be presented by number (%) by treatment arm. Primary outcome effect size will be presented as difference in medians and 95%CI, adjusted for gestational age strata based upon the quantile regression model p-values will be reported associated with 95%CI for all testable outcomes.

Primary outcome:

Modelling will use quantile regression to assess difference in median prolongation between groups. This will be supplemented by survival analysis (i.e. time until delivery), using Cox proportional hazards regression (CPH) and Kaplan-Meier survivorship curves. Survival outcomes will not be subject to hypothesis testing. For both quantile regression and survival analysis effect estimates will be presented as group difference with 95% confidence intervals (95%CI).

Secondary outcomes:

The number of events for each of the composite binary outcomes is likely to be small. An exact logistic regression model containing treatment group and gestational age strata will be used. In the event that it is not possible to obtain estimates, due to small counts each hypothesis will be tested, unadjusted for gestational strata, using Fisher's exact test. Point estimates of percentage and exact 95%CI will also be provided.

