Subgroup analyses

Gestational age at randomization has been incorporated in the prespecified primary outcome analysis. No other subgroup analyses are planned.

25. Missing data reporting and assumptions/statistical methods to handle missing data

In this study primary outcome will not have missing data, both gestational age at randomization and treatment are predetermined and all mothers will deliver in the acute in hospital setting. Based upon our experience in the PIE 1 trial (at the same institution) we expect no of missing covariate values for the three components required for analysis of the POM – group assignment, gestational age-based strata and time to delivery (delivery time – admission time). Imputation will not be performed. As described above, if an FDIU occurs it will be allocated a time of zero prolongation.

Secondary outcomes that are pre-specified for hypothesis testing use the same pre-randomization covariates and all outcomes are identifiable. If neonate is lost to follow-up the outcome will be set to missing, a sensitivity analysis will be performed to assess strength of inference given pattern of missingness by setting missing values to no event, mean event rate or event to assess dependence on inference on the unknown outcomes.

26. Additional Analyses

For the primary outcome a prespecified analysis assessing effect of absent uterine artery flow on outcome will be performed by a covariate adjusted analysis that includes treatment group, the gestational age design-based strata, fetal growth restriction (defined as an estimated fetal weight less than the 10th centile and less than the 3rd centile and absent flow on umbilical artery Doppler (UAD) examination measured at the time of randomization. The trial investigators consider that a mother with fetal growth restriction or absent UAD flow was more likely to be associated with shorter randomization to delivery times. This pre-specified covariate adjustment will increase the precision of the primary outcome measure if there is a correlation.

27. Harms

The number (and percentage) of patients experiencing serious adverse events (SAE) will be presented for each treatment arm. These are: maternal death, fetal death, event resulting threat to life of mother or baby, event that causes prolonged hospital stay, event resulting in significant disability to mother and congenital birth defect not previously detected on ultrasound. All will be listed by trial arm in

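### SAP section 11: the survival power table fits only if about 30% of women have no delivery event, and the 0.12 secondary power is not that of the planned test

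*SAP*

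**What the plan says.** SAP section 11 (Sample size) sizes the trial on median prolongation: "Power calculations settings were: 90% power, with two-sided alpha set at 0.05, median prolongation of 8.3 days in the control arm". It then gives a second table for a time-to-event analysis, "taking the median survival time of 9 days in the control group from the Hall study", with HR defined as control time over treated time. This table is described as resting on expected events, but no event probability, censoring rule or formula is given. From it the SAP concludes that "this study is not adequately powered to use survivorship as the primary endpoint", and adds: "Given the sample size of 65 per arm this study has a power of 0.9 to detect a difference of 9 days", or an HR of about 0.5.

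SAP section 25 (Missing data) says the primary outcome will have no missing values and that "all mothers will deliver in the acute in hospital setting". SAP section 14 holds the final analysis until every participant has delivered. The 65 per arm is already net of the dropout allowance of 10 per arm.

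For the two composite secondary outcomes, section 11 puts expected incidence below 0.05 and says: "At the projected sample size of 65 the power to detect a 50% change in incidence is low at 0.12". It names neither alpha nor test. SAP section 16 says: "The two secondary outcomes will each be tested at a significance level of 0.025". SAP section 24 plans exact logistic regression with treatment and gestational-age stratum, and Fisher's exact test as fallback.

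On intervals, SAP section 18 and protocol section 8.6 plan an adjusted width for the secondary outcomes. SAP section 24 nevertheless ties p-values to 95% intervals for all testable outcomes and adds: "Point estimates of percentage and exact 95%CI will also be provided". Protocol section 8.6 also pairs secondary p-values with 95% intervals.

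**The concern.** If every woman delivers under observation, events equal women. The HR table's group sizes should then equal the required events per group, but they are roughly 40% larger throughout. The table is the SAP's quantitative argument against a survival primary endpoint. A reader sets its 158 per group for 5 days beside the 65 per group for 5 days on medians, so the gap between the two approaches looks larger than it is.

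The 0.12 raises a different question: whether it is the power of the test that will be run. A reader should be able to see how little a negative secondary result would mean. The interval wording matters because a 95% interval can exclude no effect while the test at 0.025 is negative, and the report would then contradict itself.

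**Working it through.** **Inputs.** Control median 9 days, treated medians and group sizes from the SAP section 11 HR table. Allocation 1:1 (section 9). 65 analysed per arm, so 130 women. Power 90% and two-sided alpha 0.05 are stated for the median calculation; I assume they carry over, since the HR table gives no settings. (1.960 + 1.2816)² = 10.507.

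**Events required per group.** Schoenfeld: 2 × 10.507 / (ln HR)². Freedman: 0.5 × 10.507 × ((1 + HR)/(1 − HR))². HR is the unrounded ratio of medians.

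| Treated median | HR | Stated per group | Schoenfeld | Freedman | Freedman ÷ stated |
|---|---|---|---|---|---|
| 12 | 0.750 | 360 | 253.9 | 257.4 | 0.715 |
| 13 | 0.692 | 225 | 155.4 | 158.9 | 0.706 |
| 14 | 0.643 | 158 | 107.6 | 111.2 | 0.704 |
| 15 | 0.600 | 120 | 80.5 | 84.1 | 0.700 |
| 16 | 0.563 | 96 | 63.5 | 67.0 | 0.698 |
| 17 | 0.529 | 80 | 52.0 | 55.5 | 0.694 |
| 18 | 0.500 | 68 | 43.7 | 47.3 | 0.695 |
| 22.5 | 0.400 | 42 | 25.0 | 28.6 | 0.681 |

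**Reproducing the plan's figures.** With Freedman, the stated sizes imply that about 70% of women have an event in every row. With Schoenfeld, a single fraction does not fit (the ratio falls from 0.705 to 0.596). Setting 24% of controls undelivered, and 0.24^HR of treated women undelivered, gives 359, 224, 159, 121, 97, 81, 69 and 42, all close to the stated values. The stated 0.9 also follows: 0.70 × 130 = 91 events gives power 0.89 (Freedman) to 0.91 (Schoenfeld) at HR 0.5.

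**With every woman an event (130 events).**
- Power at HR 0.5. Schoenfeld: √130/2 × 0.6931 − 1.960 = 1.992, power 0.977. Freedman: √130 × 0.5/1.5 − 1.960 = 1.841, power 0.967.
- HR detectable at 90% power. Schoenfeld: exp(−2 × 3.2415/√130) = 0.566; 9/0.566 = 15.9 days, a gain of 6.9. Freedman: 3.2415/√130 = 0.2843; (1 − 0.2843)/(1 + 0.2843) = 0.557; 9/0.557 = 16.2 days, a gain of 7.2.
- Power for 5 days (HR 9/14 = 0.643). Schoenfeld: √130/2 × 0.4418 − 1.960 = 0.559, power 0.71. Freedman: √130 × 0.2174 − 1.960 = 0.519, power 0.70.

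**Secondary power.** Incidence is set at 0.05, its stated upper bound, with 65 per arm.
- Pooled normal approximation for 0.05 v 0.025 at two-sided 0.05: [0.025√65 − 1.960√(2 × 0.0375 × 0.9625)] / √(0.05 × 0.95 + 0.025 × 0.975) = (0.2016 − 0.5266)/0.2681 = −1.21, power 0.113. Counting both tails gives 0.116. This matches 0.12.
- Changing only alpha to 0.025 (critical value 2.241): (0.2016 − 0.6022)/0.2681 = −1.49, power 0.068.
- Fisher's test by full enumeration: 0.026 at alpha 0.05 and 0.010 at alpha 0.025. For a 50% rise (0.05 to 0.075), Fisher at 0.025 gives 0.017.
- For scale: with no events in one arm, Fisher at 0.025 needs 7 in the other (7 v 0 gives p = 0.013; 6 v 0 gives p = 0.028). The expected control count is 65 × 0.05 = 3.25.
- At a lower incidence, 0.03 v 0.015, Fisher at 0.025 gives 0.001.

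**Intervals.** Two tests at 0.025 correspond to 97.5% intervals. That is the width implied by the adjusted-width rule in SAP section 18 and protocol section 8.6. The 95% wording in SAP section 24 and later in protocol section 8.6 does not match it.

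**The case against.** The survival error runs in the safe direction and changes no decision. Even corrected, 5 days needs 108-112 per group against 65 analysed, survival results are not to be hypothesis-tested, and the SAP also prefers the median on grounds of clinical meaning. All of this stands. It limits the weight of the point but does not make the table or the 9-day sentence correct.

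The SAP names no formula, so the 30% is a back-calculation. That is also true. But under both standard formulas the table needs a substantial undelivered fraction. If the authors meant to censor some deliveries, such as planned ones at 34 weeks, that rule is not in the SAP and would have to be stated.

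On the secondary outcomes, 0.12 is sound arithmetic for an unstated large-sample test at 0.05. The SAP already calls this power low, and protocol section 14.2 says the trial is not powered for maternal or neonatal outcomes. Fisher is the fallback; power for the stratified exact logistic model was not computed. So the objection holds against calling 0.12 a miscalculation, but not against saying that it describes a different test.

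On intervals, an adjusted width is already planned, and the section 24 sentence on percentages may concern arm-level percentages rather than the tested effect. What remains is inconsistent wording.

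A reader might also infer that a survival analysis would beat the median regression and should be primary. The documents do not support that. The SAP says only that survival is not adequately powered, which holds at 0.70-0.71. Ranking the two methods would need an assumed distribution of prolongation that includes the 34-week delivery ceiling.

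**Conclusion.** The point holds in three parts of unequal weight.

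1. The HR table and the 9-day sentence conflict with the SAP's own statement that all women deliver. Group sizes are overstated by a factor of about 1.4 to 1.5 in the HR 0.75, 0.64 and 0.50 rows (360/254 = 1.42; 68/44 = 1.55; 68/48 = 1.42). The detectable difference at 65 per arm is about 7 days, not 9. This assumes proportional hazards, 90% power, two-sided 0.05 and delivery as the event for every woman. The SAP's conclusion that survival is underpowered for 5 days is unchanged.
2. The 0.12 does not describe the planned test. With Fisher at 0.025 and incidence at 0.05, power is about 0.01 for a halving and 0.02 for a 50% rise; changing only alpha gives 0.07 for a halving. That the SAP used a large-sample test at 0.05 is inferred from the match. It would be too strong to say that both stated power figures are wrong: the first is, while the second is correct for a test the plan does not use.
3. The interval wording is internally inconsistent; the rule itself is in place.

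No design decision turns on any of this, but the stated power is what readers will use to interpret supplementary and secondary results.

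**What to change.** - SAP section 11, HR table: state the formula and an event fraction of 1, and recompute every row (HR 0.75, 0.64 and 0.50 become about 254-258, 108-112 and 44-48 per group). If a lower fraction is intended, state the censoring rule and reconcile it with sections 14 and 25.
- SAP section 11, sentence after the table: say that 65 per arm gives 90% power at HR 0.56-0.57, about 7 days on a 9-day median, and about 0.70-0.71 power for 5 days under proportional hazards. Keep the conclusion that survival is not adequately powered for 5 days.
- SAP section 11, secondary power: name alpha, test, baseline incidence and direction of change, and give the power for the planned exact test at 0.025. Until the stratified exact model is evaluated, Fisher's values (about 0.01 and 0.02) can stand in, labelled as such.
- SAP section 24 and protocol section 8.6: specify 97.5% intervals for the two tested secondary effects, and say whether the exact 95% intervals refer to arm percentages only.

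The cost is wording and a short recalculation. Sample size, conduct and primary analysis are unaffected. The survival figure becomes more favourable and the secondary figure less so.

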### 6.2.2. Composite neonatal outcome:

- The occurrence of any of the following serious neonatal outcomes:
  - Neonatal death within 6 weeks after the due date
  - Grade III or IV intraventricular haemorrhage defined on imaging as enlarged ventricles associated with haemorrhage or when the haemorrhage extends into the cerebral tissue around the ventricles
  - Necrotizing enterocolitis diagnosed on radiographic studies
  - Bronchopulmonary dysplasia defined as needing oxygen at day 28 of life, either on a ventilator, by CPAP or via a nasal catheter
  - Significant neonatal sepsis as defined by the attending paediatrician.

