## 8.6 Statistical methods

The patient characteristics at randomization, by treatment group, will be presented as mean (SD), median [25th – 75th percentile], minimum, maximum and count (%) depending upon type and distribution. The distribution of baseline characteristics between treatment groups will not be subject to hypothesis testing.

The primary outcome will be measured from the time of randomisation to delivery. Secondary maternal and neonatal outcomes will be measured from the time of recruitment until six weeks after the due date. The significance level for the primary outcome is set at 0.05 and all hypothesis testing will be two-sided. If, and only if, there is a significant difference for the primary outcome, the two secondary outcomes will be tested at a significance level of 0.025. Standard 95% confidence interval (CI) will be used to present the analysis of the primary outcome. The width of the CI used will be adjusted for the secondary outcomes if tested. For raw results data, the primary outcome will be summarized using median [25th – 75th percentile] along with minimum and maximum values.

All secondary outcomes and exploratory outcomes of interest will be presented by number (%) by treatment arm. Primary outcome effect size will be presented as difference in medians and 95% CI, adjusted for gestational age strata based upon the quantile regression model. P-values will be reported with associated with 95% CI for the secondary outcomes if tested. Exploratory outcomes will be presented with 95% CI.

Modelling will use quantile regression to assess difference in median prolongation between groups. This will be supplemented by survival analysis (i.e. time until delivery), using Cox proportional hazards regression (CPH) and Kaplan-Meier survivorship curves. Survival outcomes will not be subject to hypothesis testing. For both quantile regression and survival analysis effect estimates will be presented as group difference with 95% CI.

The number of events for each of the composite binary outcomes is likely to be small. An exact logistic regression model containing treatment group and gestational age strata will be used. In the event that it is not possible to obtain estimates, due to small counts each hypothesis will be tested, unadjusted for gestational strata, using Fisher's exact test. Point estimates of percentage and exact 95%CI will also be provided.

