## **Follow-up procedures**

All participants will be followed from enrolment until their discharge from hospital after delivery and all data will be recorded.

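### SAP 14 sets the earliest analysis at six weeks after the last recruited patient's delivery, but the neonatal death window closes six weeks after the due date, 6 to 14 weeks later for these births

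*SAP*

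**What the plan says.** SAP 14 (Timing of final analysis) makes three statements. Its opening sentence is a condition: "Unblinding and final analysis will be performed only after all participants have being delivered and all neonatal follow-up has been completed". It then says that neonatal death, as part of the neonatal composite, "is assessed at six weeks post-delivery". From that it derives a floor: "analysis is will not commence prior to six weeks after the delivery of the last recruited trial patient".

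Four other places end the window at a different point:

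- SAP 15: "Secondary maternal and neonatal composite outcomes are measured from time of recruitment until six weeks after the due date".
- SAP 23, in the neonatal composite: "neonatal death within 6 weeks after the expected due date".
- Protocol 6.2.2: "Neonatal death within 6 weeks after the due date".
- Protocol 8.6: "Secondary maternal and neonatal outcomes will be measured from the time of recruitment until six weeks after the due date".

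Protocol 11.1 (Follow-up procedures) gives a third end point: "All participants will be followed from enrolment until their discharge from hospital after delivery and all data will be recorded".

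SAP 10 adds that the randomisation list reaches the researchers only after the data are locked, neonatal follow-up included.

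**The concern.** Six weeks after birth and six weeks after the due date are the same day only for a baby born on its due date. This trial enrols at 26+0 to 31+6 and usually delivers by 34 weeks, so in normal conduct the two never coincide. SAP 14 therefore dates the earliest analysis from an end point that the outcome definition does not use.

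The outcome at stake is the neonatal composite. It is one of only two secondary outcomes eligible for formal testing (SAP 16), each at 0.025 and only if the primary outcome is significant. SAP 11 expects secondary incidence below 0.05, which is at most about 65 × 0.05 = 3.25 events per arm. With so few events, the closing date of the window should not be open to interpretation, and unblinding cannot be undone.

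**Working it through.** **Inputs**

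- Enrolment at 26+0 to 31+6 (protocol 5.2).
- Expectant management usually ends at 34 weeks (protocol 7.3.1).
- Analysis floor: 6 weeks after delivery (SAP 14).
- Window: 6 weeks after the due date (SAP 15 and 23, protocol 6.2.2 and 8.6).
- Gestation at the due date: not stated. Assumed 40+0, with 39+0 and 41+0 as the range.
- 150 women (protocol 4.4) over 2 to 3 years (protocol, Duration of the project). Even accrual is assumed.

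**Check on the documents' own figure.** From 31+6 to 34+0 is 15 days, which matches the ceiling in SAP 11. The 63-day and 42-day maxima given there for the two strata fit delivery at 35+0 instead (26+0 to 35+0 and 29+0 to 35+0), so 35+0 is included as a variant.

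**Window length.** Weeks from birth to closure = 40 − GA + 6. Shortfall of the six-week floor = 40 − GA.

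| Gestation at birth | Window closes after birth | Floor too early by |
|---|---|---|
| 26+0 | 20w+0d | 14w+0d |
| 26+2 | 19w+5d | 13w+5d |
| 29+0 | 17w+0d | 11w+0d |
| 31+6 | 14w+1d | 8w+1d |
| 34+0 | 12w+0d | 6w+0d |
| 35+0 (variant) | 11w+0d | 5w+0d |

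For births at 26+0 to 34+0, a due date at 39+0 gives closure at 11 to 19 weeks, and 41+0 gives 13 to 21 weeks.

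With the planning medians of 8.32 and 13.32 days, closure falls at 18.8 and 18.1 weeks after birth for enrolment at 26+0, and at 13.0 and 12.2 weeks for enrolment at 31+6.

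**Babies with an open window at the floor.** If the last recruited patient delivers at time T, the floor is T + 6 weeks. A baby born at time b and gestation GA is still in its window if b + 46 − GA > T + 6, that is, if it was born within 40 − GA weeks before T. Accrual is 150/36 = 4.17 or 150/24 = 6.25 births per month.

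- All births near 30 weeks: 10 weeks = 2.30 months, giving 4.17 × 2.30 = 9.6 to 6.25 × 2.30 = 14.4, or roughly 10 to 14 babies.
- Outer bounds: 4.17 × 1.38 months (6 weeks, all births at 34+0) = 6, and 6.25 × 3.22 months (14 weeks, all births at 26+0) = 20.

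**Events.** At the SAP's ceiling of 0.05, 14 babies would have at most 0.7 composite events and 20 babies at most 1.0 over the whole window. Fewer would fall after the floor, because part of the window has passed by then and bronchopulmonary dysplasia is determined at day 28.

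**The case against.** The strongest reply is that SAP 14 already protects the outcome. Its first sentence holds back unblinding and analysis until all neonatal follow-up is done, SAP 10 ties release of the list to the same condition, and the six-week clause is only a floor. Read with the due-date definition used in four other places, these conditions would block an analysis at six weeks. That stands as far as it goes: a reader might infer that the SAP simply permits unblinding at six weeks, and the documents do not support that. They do leave a gap. The condition depends on when follow-up counts as complete, and the only end point that SAP 14 itself gives for neonatal death is six weeks after birth. SAP 15 also allows timing to vary by outcome measure, although SAP 23 is specific about neonatal death.

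A reader might also infer that follow-up to discharge favours metformin, because babies born later may go home sooner. This is not supported. Participants in protocol 11.1 may mean the mothers only, the documents give no discharge times, and the due-date end point itself gives later-born babies less postnatal observation (12 weeks at 34+0 against 20 at 26+0). Protocol 8.6 and SAP 24 and 25 also plan a sensitivity analysis for neonates lost to follow-up, which suggests that neonatal follow-up is meant to extend beyond discharge.

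It is also fair to say that the practical effect is small. An open window is not a missed event. The composite is tested only after a significant primary result, SAP 11 puts the power for secondary outcomes at 0.12, and protocol 14.2 says that the trial is not powered for neonatal benefit.

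**Conclusion.** SAP 14 is wrong as written: it contradicts SAP 15, SAP 23 and protocol 6.2.2 and 8.6 on when neonatal death is assessed, and it takes its earliest analysis date from the discrepant end point. The floor is 6 to 14 weeks too early, assuming a due date at 40+0 and birth between 26+0 and 34+0. Shifting the due date by a week moves both ends by a week. The 14-week end is an extreme, since eligibility requires that delivery is not expected within 48 hours, and births after 34 weeks would lower the other end.

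A team that judged completion by SAP 14 alone could lock the data while roughly 10 to 14 babies were still in their windows (outer range 6 to 20, under even accrual), with few if any events missed. This is an inconsistency to settle before database lock. It does not threaten the primary analysis.

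**What to change.** In SAP 14, state that neonatal death is assessed at six weeks after the expected due date. Set the earliest database lock, unblinding and analysis at six weeks after the latest expected due date among all randomised women. The reference should be all randomised women, because the last woman recruited or delivered need not have the latest due date.

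In protocol 11.1, say whether follow-up to discharge refers to mothers, babies or both, and give the due-date end point for ascertaining neonatal survival. Protocol 5.1 already plans a contact six weeks after the due date for women with unclassified proteinuric hypertension; a similar contact could serve for every baby.

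The cost is a few sentences, one contact or record check per baby, and a delay of up to about 14 weeks. That is an upper bound: any woman randomised by the time the last one is recruited is at least 26+0, so her due date is at most 40 − 26 = 14 weeks away.
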